
- Death from any cause during hospitalization for surgery

Assessment of an effect on patient reintubation:

- Reintubation due to respiratory failure (ARF)
- Reintubation due to non-respiratory failure, excluding reintubations specifically for a new surgical or interventional radiology procedure
- Time to reintubation to assess delayed reintubation (characterized by a non-significant difference in reintubation rate between groups but a longer delay in the NIV group)

Assessment of an effect on length of stay in ICU and duration of invasive or non-invasive mechanical ventilation:

- Number of days of invasive mechanical ventilation (intubated or tracheostomized) during hospitalization for surgery, including episodes of reintubation
- Number of days of non-invasive mechanical ventilation (NIV) during hospitalization for surgery, including prophylactic and therapeutic NIV.

**Assessment of an effect on the incidence of healthcare-associated infections, defined according to
Centers for Disease Control (CDC) criteria:**

- Infectious pneumonia: see secondary endpoint criteria
- Urinary tract infection: fever $> 38^{\circ}\text{C}$ and urine culture showing no more than two microbial species, at least one with a concentration $> 10^5 \text{ CFU/ml}$, in a patient with no other obvious source of infection
- Catheter-related infection: fever $> 38^{\circ}\text{C}$, positive catheter culture or sample, and resolution of fever within 48 hours after catheter removal without antibiotic change and no other identified source of infection
- Bacteremia: fever $> 38^{\circ}\text{C}$ and at least one positive blood culture (two or more if coagulase-negative staphylococcus)
- Surgical site infection

Data collection is performed prospectively throughout the first 7 days of hospitalization for surgery.

D) Description of Investigational Medicinal Products

MEDICAMENTS :

Name of the Medicinal Product (INN)	Brand Name	Pharmaceutical Form	Route of Administration	Dosage per Administration
Medical Liquid Oxygen	N/A	Gas	N/A	

Therapeutic regimen:

The ventilatory mode used will be an assisted mode (PSV or BiPAP), as these have shown a stronger (86) and more sustained effect (29) than CPAP alone.

The interface—nasal mask, face mask, or helmet—is chosen according to the unit's usual practice.

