NIV sessions of 1 hour are repeated every 2 to 3 hours, aiming for a daily assistance duration of 6 to 8 hours for a minimum of 24 hours. Weaning from NIV is managed by the clinician within a maximum of 48 hours.

Initially set between +5 and +8 cmH₂O, IPAP is gradually increased in increments of 2 to 3 cmH₂O for patient comfort, until achieving an inspiratory peak allowing an expired tidal volume (Vte) between 6–8 ml/kg of predicted body weight, according to current ventilation recommendations (84, 112), with a respiratory rate $< 30/\text{min}$.

PEEP is set between +5 and +10 cmH₂O, and FiO₂ adjusted to maintain SpO₂ $> 92\%$ or PaO₂ $> 70 \text{ mmHg}$ on blood gas analysis. Care is taken to ensure that total pressure (PEEP + IPAP) remains $\leq 20 \text{ cmH}_2\text{O}$ to avoid gastric distension (airway pressure lower than the lower esophageal sphincter pressure) (42) and to minimize the theoretical risk of bronchial suture dehiscence in thoracic surgery.

The ventilator's inspiratory trigger is set to the minimum value allowing the most sensitive detection of inspiratory efforts without causing auto-triggering.

The clinician may adjust IPAP based on the patient's blood gas results.

Duration of Treatment:

Each prophylactic NIV session lasts 1 hour. Sessions are repeated every 2 to 3 hours, separated by 2-hour periods without assisted ventilation to allow the patient to rest, eat, and receive care, including physiotherapy sessions. This schedule may be adapted to the unit's activity, with the goal of achieving a daily assistance duration of 6 hours without exceeding 8 hours, for a minimum of 24 hours.

Weaning from NIV is managed by the clinician within a maximum of 48 hours.

Expected outcomes:

Prevent the occurrence of PPCs and the complications they cause:

- Infectious pneumonia and aspiration pneumonia
- Pleural effusions
- Atelectasis
- Bronchospasm
- Acute respiratory failure (ARF) and hypoxemia, and consequently:
 - Prevent patient reintubation
 - Prevent surgical site infections and anastomotic suture dehiscence
 - Reduce morbidity and mortality related to reintubation, and shorten length of stay
 - Avoid the need for invasive mechanical ventilation and all associated complications:
 - Nosocomial infections, including ventilator-associated pneumonia (VAP) due to micro-aspirations linked to the endotracheal tube
 - Delayed rehabilitation
 - Communication difficulties
 - Discomfort

E) CONSIDERATIONS STATISTIQUES

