Statistical analyses will be performed using R software and IBM SPSS.

A total of 266 patients are planned for inclusion, divided into two balanced groups.

DESCRIPTION OF PLANNED STATISTICAL METHODS:

Research Protocol

Patients will be analyzed on an intention-to-treat basis and then per-protocol.

Intention-to-treat analysis: all patients included in the study for whom outcome data are available will be considered in the analysis according to their randomization group. No imputation method will be used in case of missing data.

If organizational constraints prevent the patient from receiving prophylactic NIV (despite inclusion in the corresponding intervention arm), the patient will remain in their randomization arm for the entire study duration, and their data will be analyzed on an intention-to-treat basis.

Per-protocol analysis excludes patients for whom the initial protocol was not fully adhered to. Only patients who followed the protocol will be considered in the analyses, within the arm to which they were originally randomized.

The analysis will focus on the primary endpoint to determine whether randomization to the "PPC prevention strategy" arm leads to a reduction in PPC frequency compared to the control group. Effect size and number needed to treat will be calculated.

Similarly, for secondary endpoints, significant differences between the two groups will be sought in terms of:

- a) Safety and tolerability of the strategy under study (see safety assessment parameters)
- b) Mortality during hospitalization
- c) Patient reintubation
- d) Length of stay and duration of invasive or non-invasive mechanical ventilation

Description of the overall analysis method

The significance threshold is set at 0.05, and all tests will be two-sided. For qualitative variables, results will be reported as counts and percentages. For quantitative variables, results will be reported as means and standard deviations in case of normal distribution, and as medians with 25th and 75th percentiles in the absence of a Gaussian distribution. Normality of continuous variables will be assessed using the Kolmogorov-Smirnov test.

A simple descriptive analysis will be performed on the entire study population and by subgroups. This description will include sociodemographic data, medical history, ongoing treatments, etc.

A qualitative and quantitative analysis of missing data will be performed. No imputation of missing data is planned for the endpoints.

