Study of Associations (Qualitative and/or Quantitative Variables):

For each parameter of interest, a bivariate analysis will be performed, possibly complemented by a multivariate analysis adapted to the outcome variable to explore potential associations.

For bivariate analyses, the use of parametric or non-parametric tests will depend on sample size and/or variable distribution. The significance threshold is set at 0.05, and all tests will be two-sided.

The statistical test used will be Pearson's Chi-square test (or Fisher's exact test) for qualitative variables. For quantitative variables, the statistical tests used will be ANOVA or the non-parametric Kruskal-Wallis test.

The association between each presumed risk factor and the parameter of interest will be estimated using the relative risk (RR) and its 95% confidence interval.

A multivariate logistic regression analysis will estimate the adjusted RR and its 95% confidence interval for each retained factor (conservative threshold of 0.20 in univariate analysis).

Early Mortality:

Overall survival is defined as the time between the date of operating room discharge and the date of death if the patient dies within 7 days, or the end of study follow-up at Day 7. The Kaplan-Meier method will be used to estimate survival rates and plot survival curves. The Log-Rank test will be used to compare survival curves. Event-free survival is defined as the time between operating room discharge and the date of occurrence of the event (PPC) or the date of last follow-up if censored.

A semi-parametric Cox proportional hazards regression model will estimate for each variable the crude association (Hazard Ratio, HR) between the factor studied and death (bivariate analysis), then the adjusted HR in multivariate analysis.

The significance threshold for including other variables in the multivariate analysis will be 0.20. If several candidate variables are redundant, the most representative variable will be retained for the model.

Subgroup Analyses (Exploratory):

Subgroup analyses will address the occurrence of endpoints:

- According to patient characteristics at inclusion (medical history, ARISCAT score components, type of surgery, and planned anesthetic technique).
- The subgroup of patients receiving NIV as curative (under conditions noted at session start) will be compared to the group receiving NIV only prophylactically in terms of outcome at Day 7.

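### The between-arm comparison of NIV days counts the assigned prophylactic NIV as outcome, so at the planning rates it will very likely show more NIV in the NIV arm even if therapeutic NIV is halved

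*Combined protocol and SAP*

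**What the plan says.** All references are to the combined protocol and SAP.

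- **Section C, secondary endpoints.** Under a heading that announces an "Assessment of an effect on length of stay in ICU and duration of invasive or non-invasive mechanical ventilation", the NIV measure is a single count of days on NIV during the surgical stay, "including prophylactic and therapeutic NIV". Data are collected over the first 7 days of the surgical stay.
- **Section E, planned statistical methods.** For secondary endpoints, "significant differences between the two groups will be sought in terms of" a list whose item d is "Length of stay and duration of invasive or non-invasive mechanical ventilation". The count is therefore tested between arms and not merely tabulated.
- **Section D, duration of treatment.** The NIV arm is assigned prophylactic sessions "with the goal of achieving a daily assistance duration of 6 hours without exceeding 8 hours, for a minimum of 24 hours". The upper limit is set by "Weaning from NIV is managed by the clinician within a maximum of 48 hours".
- **Section E, exploratory subgroup analyses.** Patients "receiving NIV as curative (under conditions noted at session start") are compared with those who had only prophylactic NIV, on outcome at Day 7.
- **Section E, planned methods and selection of patients.** NIV-arm patients who cannot be given prophylactic NIV for organizational reasons stay in their arm for the intention-to-treat analysis.

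**The concern.** A patient treated as assigned in the NIV arm accrues one to two NIV days before anything has gone wrong. A control patient accrues NIV days only when NIV is used therapeutically. The total therefore mixes two quantities: the treatment given, and the later need for ventilatory support that the treatment is meant to reduce. The first can outweigh the second.

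The likely result is a significant excess of NIV days in the NIV arm in a trial where prophylaxis works. Read under a heading about effect, that looks like harm or added burden. The useful question, whether fewer patients need therapeutic NIV or need it for less time, has no comparison by randomized arm. The exploratory subgroup does not supply one: it is formed after randomization and contrasts types of NIV use, not arms.

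**Working it through.** The plan gives no figure for NIV days, so there is none to reproduce.

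**Inputs from the document**
- Prophylactic days per treated patient, P: 1 to 2 (24 to 48 hours, section D).
- ARF rates: 30% control and 15% NIV (sample-size section). The control range given there is 30–50%; its upper end with the planned 50% relative reduction gives 50% and 25%.
- Window: 7 days.
- Test: ANOVA or Kruskal-Wallis, two-sided 5%.
- Size: 121 per arm, used here only as the number analysed.

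**Assumptions (not in the document)**
- D, mean therapeutic NIV days per ARF patient, the same in both arms.
- c, the share of the NIV arm that receives prophylactic NIV.

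**Step 1: expected totals.** NIV arm: c·P + p_NIV·D. Control: p_ctl·D. The difference is c·P − (p_ctl − p_NIV)·D.

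At 30% vs 15% and c = 1:
- P = 1: D = 2, 3, 5 gives 1 − 0.15·D = +0.70, +0.55, +0.25 days.
- P = 2: the same D gives +1.70, +1.55, +1.25 days.

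In each case therapeutic days are halved; at D = 3 they are 0.30 × 3 = 0.90 against 0.15 × 3 = 0.45.

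**Step 2: break-even.** Totals are equal when D = c·P/(p_ctl − p_NIV). At 30% vs 15% and c = 1, this is 1/0.15 = 6.7 days or 2/0.15 = 13.3 days. The first nearly fills the window and the second exceeds it.

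These sums add the two kinds of NIV. The plan does not say how a day with both is counted. If every ARF patient's therapeutic NIV fully overlapped the prophylactic days, break-even would be 0.85/0.15 = 5.7 days (P = 1) or 1.70/0.15 = 11.3 days (P = 2), so the conclusion is unchanged.

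**Step 3: how often the test would show it.** 1,000 simulated trials per row, 121 per arm, D uniform on 1–5 days (mean 3), Kruskal-Wallis. The last column counts trials with p < 0.05 and a higher mean total in the NIV arm.

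| ARF control vs NIV | P | c | Break-even D | Mean difference at D = 3 | Significantly more NIV days in NIV arm |
|---|---|---|---|---|---|
| 30% vs 15% | 1 | 100% | 6.7 | +0.55 | 99.9% |
| 30% vs 15% | 1 | 80% | 5.3 | +0.35 | 96.9% |
| 30% vs 15% | 1 | 60% | 4.0 | +0.15 | 78.5% |
| 30% vs 15% | 2 | 100% | 13.3 | +1.55 | 100% |
| 30% vs 15% | 2 | 60% | 8.0 | +0.75 | 99.3% |
| 50% vs 25% | 1 | 100% | 4.0 | +0.25 | 86.9% |
| 50% vs 25% | 1 | 80% | 3.2 | +0.05 | 49.5% |
| 50% vs 25% | 1 | 60% | 2.4 | −0.15 | 11.0% |
| 50% vs 25% | 2 | 100% | 8.0 | +1.25 | 100% |
| 50% vs 25% | 2 | 60% | 4.8 | +0.45 | 61.4% |

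**Step 4: therapeutic days alone, same simulations.** At 30% vs 15% the fall is 0.45 days, detected in 78–81% of trials. At 50% vs 25% it is 0.75 days (1.50 against 0.75), detected in 97–98%.

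**The case against.** **The total may be deliberate.** The endpoint says openly that both kinds of NIV are included, and total exposure is a fair measure of the ventilation burden of a strategy. That stands, and is a reason to keep the count. It does not make the count a measure of effect, which is how section C frames it and section E tests it.

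**The direction is not guaranteed.** A reader might infer that every NIV-arm patient receives 24 to 48 hours of NIV and that the comparison must go against NIV. The documents do not support that. They provide for non-delivery under intention-to-treat, make intolerance an endpoint, and plan an analysis of premature discontinuation. At 50% vs 25% with P = 1, D = 5 and full delivery, the mean difference is 1 − 0.25 × 5 = −0.25 days, in favour of NIV. The tests are also two-sided and the objective presumes no direction. This objection stands as a limit on certainty.

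**Benefit can be seen elsewhere.** It can. The adjudicated primary endpoint, reintubation, time to reintubation and invasive-ventilation days do not count the assigned NIV. The trial is not blind to benefit; this one count is.

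**Therapeutic NIV has its own weakness.** The trial is open-label, and calling a session curative is a judgement by unblinded staff, hardest when a patient deteriorates during the prophylactic period. The total is immune to that misclassification. This stands, and the fix must deal with it.

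**Conclusion.** The endpoint should not be tested between arms as a measure of effect in its present form. At the planning ARF rates with full delivery, it will very likely show significantly more NIV days in the NIV arm while therapeutic NIV is halved: an excess of 0.55 to 1.55 days at an assumed mean of 3 therapeutic days, significant in over 99% of simulated trials. At 80% delivery and one prophylactic day the figure is still about 97%. It weakens with poorer delivery, and at 50% vs 25% ARF with one prophylactic day it can fall away or reverse. The length of therapeutic NIV and the delivery rate are assumptions, since the document gives neither.

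The defect is confined to one secondary endpoint; the primary endpoint and sample size do not depend on it.

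A reader might extend the point to ICU stay, because the intervention is delivered in intensive care. The documents do not support that. They do not say where control patients are cared for or how many enter the ICU under standard care, the bullets under the heading define no ICU-day measure, and nothing shows that planned and unplanned ICU days are recorded separately. It remains an assumption and forms no part of this conclusion.

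**What to change.** 1. Make therapeutic (curative) NIV the between-arm effect comparison, by randomized arm, as days, as the proportion of patients needing it, or both.
2. Before the data are analysed, write one objective definition of curative NIV for classifying sessions and apply it identically in both arms, including during the prophylactic period.
3. Keep total NIV days as a descriptive measure of exposure or resource use, and state that it is not read as an effect.
4. Report prophylactic NIV in the NIV arm as adherence.

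**Cost.** The statistical change is wording in the endpoint list and item d. Whether new data are needed is open: the only sign that the purpose of NIV is captured is the remark in the subgroup section about conditions noted when a session starts. The sponsor must confirm that this is recorded for every NIV session in both arms; if not, the case report form needs a field. The remaining downside is unblinded classification, which an objective definition reduces but does not remove. Showing the descriptive total beside the therapeutic comparison lets a reader see whether sessions may have been relabelled.

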SYNOPSIS

PROTOCOL AnticipUSC – N°ICO 2016-A-04

A) Clinical Trial Identification

TITLE OF THE TRIAL: *Multicenter, open-label, randomized study comparing early postoperative prophylactic non-invasive ventilation in the intensive care unit versus standard postoperative follow-up in patients at high risk of postoperative pulmonary complications according to the preoperative ARISCAT score, undergoing surgery under general or regional anesthesia (ANTICIPUSC)*

SHORT TITLE: ANTICIPUSC

COORDINATOR: [name] [name]

ESTIMATED NUMBER OF CENTERS: 3

NUMBER OF PATIENTS: 266

B) Sponsor Identification

NAME OF THE ORGANIZATION: ICO, DRCI-Cellule de Promotion

CONTACT PERSON: MME [name]

[contact]

[contact]

C) General Information About the Trial

Indication:

This study will focus on a selected population at high risk of postoperative pulmonary complications (PPC) according to the ARISCAT score, among all surgical patients in the participating centers, whether undergoing surgery under General Anesthesia (GA) or Regional Anesthesia (RA), who may benefit from preventive postoperative management.

Primary objective:

The primary objective of the study is to compare the effectiveness of a preventive postoperative management strategy using non-invasive ventilation (NIV) in the intensive care unit versus standard care, on the incidence of acute respiratory failure within 7 postoperative days during hospitalization, in patients at high risk according to the ARISCAT score.

Secondary objectives:

- The safety and tolerability of the strategy under study
- The cause of acute respiratory failure (arf) among the different postoperative pulmonary complications (ppc)
- Mortality during hospitalization for surgery, up to a maximum of 7 days
- Any effect on patient reintubation (cause and timing)
- Any effect on the length of stay in the icu/intensive care unit and on invasive or non-invasive mechanical ventilation
- Any effect on the incidence of healthcare-associated infections, defined according to the centers for disease control (cdc) criteria.

Inclusion criteria:

1. Patient aged 18 years or older
2. Patient scheduled for elective surgery or considered semi-urgent (pre-anesthesia consultation < 48 hours before the surgical procedure), under General Anesthesia (GA) or Regional Anesthesia (RA)
3. Patient with an ARISCAT score greater than or equal to 45 (high risk of PPC)
4. Written informed consent signed by the patient

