- Identification of factors associated with failure of prophylactic NIV in the subgroup where NIV was prematurely discontinued.

Statistical Justification for Sample Size:

Previously described data indicate that the expected effect size is approximately a 50% reduction in events:

- In studies on medical populations, the effect of prophylactic NIV was observed even on harder endpoints than ours: -66% reduction in reintubation, -51% reduction in ARF incidence, and -50% reduction in reintubations, and again -69% reduction in ARF incidence.

- In surgical populations, prophylactic NIV has led to a reduction in restrictive syndrome of about 50%, an improvement in pulmonary function tests (PFTs) of +30%, and a decrease in length of stay by 7 days.
- In curative use after abdominal surgery—a more unfavorable situation since ARF is more advanced—Squadrone reported favorable outcomes in 90% of cases with CPAP, and reintubations were reduced by 30%.

Given that the expected incidence of ARF in the high-risk group is 30–50%, a sample size of at least 121 subjects per arm is required to demonstrate, under a two-sided hypothesis, a relative reduction of 50% in ARF between a group managed with prophylactic NIV (15%) and a group managed with standard care (30%), with an alpha risk of 5% and a beta power of 90%. We anticipate 10% of patients will be non-evaluable.

The required sample size is therefore $242 + 24 = 266$ high-risk subjects evaluated for PPC.

STATISTICAL STOPPING RULES:

No interim analysis is planned in the protocol. However, if during the review of safety and efficacy data provided to the independent monitoring committee (raw, descriptive, and summarized data without pre-established statistics by the investigator or sponsor), a highly significant difference is identified for the primary endpoint or one of the safety parameters when comparing the two groups blinded to treatment allocation, the committee may decide to stop the study.

METHOD FOR HANDLING MISSING, UNUSED, OR INVALID DATA:

Patients included in the study for whom an endpoint is not available will not be considered in the analysis for that missing endpoint. No imputation method will be used for missing data.

MANAGEMENT OF CHANGES TO THE INITIAL ANALYSIS PLAN:

Modifications to the initial analysis plan may be proposed by the monitoring committee (interim analysis, statistical tests, adverse events, secondary objectives) if new literature data justify them.

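### Ventilation days and length of stay are cut off at Day 7, with no definition of length of stay and no rule for deaths or unfinished stays

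*Combined protocol and SAP*

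**What the plan says.** Under Secondary endpoints (section C), two durations are defined: "Number of days of invasive mechanical ventilation (intubated or tracheostomized) during hospitalization for surgery, including episodes of reintubation" and "Number of days of non-invasive mechanical ventilation (NIV) during hospitalization for surgery, including prophylactic and therapeutic NIV". Neither carries a time limit.

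Length of stay has no such definition. It appears as a secondary objective, "Any effect on the length of stay in the icu/intensive care unit and on invasive or non-invasive mechanical ventilation", and in the endpoint heading, "Assessment of an effect on length of stay in ICU and duration of invasive or non-invasive mechanical ventilation", but no bullet beneath that heading says what is counted, from when, or until when. The list of planned between-group comparisons in section E includes it without saying ICU or hospital, and Expected outcomes (section D) also leaves it unqualified.

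The observation window is short and stated consistently. The secondary endpoints close with "Data collection is performed prospectively throughout the first 7 days of hospitalization for surgery"; the Early Mortality paragraph refers to "the end of study follow-up at Day 7"; section F gives a 7-day follow-up period. Among the secondary objectives, only mortality is explicitly limited to 7 days.

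For quantitative variables, Study of Associations (section E) offers "ANOVA or the non-parametric Kruskal-Wallis test". Missing endpoints are neither imputed nor analysed. Censoring is described only for the survival analyses.

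**The concern.** An endpoint that runs over the hospitalisation cannot be computed for a patient whose ventilation or stay continues after data collection stops. Those are the patients who contribute most to total duration. The plan does not say whether such a patient enters with the value reached at Day 7 or is set aside as missing. The first choice compresses the difference between arms. The second removes the sickest patients.

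Death raises a separate problem. A patient who dies on Day 2 has few ventilation days and a short stay. In a plain comparison of durations, that counts in favour of the patient's arm.

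At stake are the size and interpretation of any reported effect on stay or ventilation, and in some scenarios the power to see one. The primary endpoint is not affected.

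**Working it through.** **Inputs.** From the documents: a 7-day window; 121 patients per arm (Statistical Justification for Sample Size); a rank test, since Kruskal-Wallis with two groups is the rank-sum test. Assumed, because the documents give no mean, median or SD for any stay: log-normal stay with the medians below and an SD of log-stay of 0.5 (0.8 in one row). The plan contains no calculation for these endpoints, so there is no figure of its own to reproduce.

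**Step 1: formulas.** For median m and log-SD s:

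- full mean = m × exp(s²/2)
- share at the cap = Φ(ln(m/7)/s)
- mean cut at 7 days = m × exp(s²/2) × Φ((ln(7/m) − s²)/s) + 7 × Φ(ln(m/7)/s)

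**Step 2: one case in full.** Take medians of 10 and 8 days with s = 0.5, so exp(0.125) = 1.133.

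- Full difference: (10 − 8) × 1.133 = 2.27 days.
- Shares at the cap: Φ(0.713) = 0.762 and Φ(0.267) = 0.605, averaging 68%.
- Means cut at Day 7: 6.61 and 6.25, a difference of 0.36 day.

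**Step 3: range.** Power is from 1,500 simulated trials per row, two-sided 5%. The Monte Carlo error near 80% is √(0.8 × 0.2/1500), about 1 percentage point.

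| Medians (days) | log-SD | At cap, both arms | Mean difference, full | Mean difference, cut at Day 7 | Power, full | Power, cut at Day 7 |
|---|---|---|---|---|---|---|
| 3 vs 2.4 | 0.5 | 3% | 0.68 | 0.62 | 91% | 91% |
| 4 vs 3.2 | 0.5 | 9.5% | 0.91 | 0.72 | 91% | 91% |
| 4 vs 3.2 | 0.8 | 20% | 1.10 | 0.57 | 53% | 52% |
| 5 vs 4 | 0.5 | 19% | 1.13 | 0.74 | about 90% | about 90% |
| 10 vs 8 | 0.5 | 68% | 2.27 | 0.36 | 92% | 80% |
| 15 vs 13 | 0.5 | 91% | 2.27 | 0.07 | 57% | 23% |
| 16 vs 9 | 0.5 | 82% | 7.93 | 0.48 | 100% | 100% |

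The part of the true mean difference that survives the cut runs from 0.62/0.68 = 91% down to 0.07/2.27 = 3%. The last row shows that power and estimate can part company: the test still succeeds, but a 7.93-day difference is reported as 0.48 day.

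**Step 4: deaths.** Consider three ICU patients: one dies on Day 2, one is discharged alive from ICU on Day 4, one is still there at Day 7. As plain stays they score 2, 4 and 7 days, so the death ranks best. As days alive and out of ICU to Day 7, with death scored 0, they score 0, 7 − 4 = 3, and 0, so the survivor discharged on Day 4 ranks best.

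**Step 5: ventilation days.** The documents give no basis for a distribution, so only the location of the cut can be described. Section D limits weaning from prophylactic NIV to 48 hours, so those days should normally fall inside the window. The cut falls on late or prolonged reintubation, tracheostomy and prolonged therapeutic NIV.

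**The case against.** The strongest reply is that seven days is the deliberate horizon of the whole trial: primary endpoint, mortality, data collection and follow-up all use it. The sentence on data collection closes the entire list of secondary endpoints and can be read as setting their window. Days within a 7-day window are a legitimate restricted measure. Where the text names a type of stay, it is ICU stay, which may well be short, and the short-stay rows show almost no loss of power. Deaths are analysed separately by Kaplan-Meier and log-rank, so an excess would be visible. The text is also a synopsis, and it does not say whether later discharge dates are recorded.

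Much of this stands. A 7-day restriction is defensible, and the large power losses come only from assumed long stays. But the plan does not state the restriction for these endpoints, and the ventilation-day wording says otherwise. A separate mortality analysis does not change how a death is scored in the duration comparison. The shrinkage of the mean difference is present even for short stays.

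A reader might also infer that the plan expects a 7-day reduction it could never observe, since section E cites "a decrease in length of stay by 7 days". The documents do not support this. The figure is background from earlier surgical populations, offered in support of a roughly 50% reduction in events. It is not a target here, and the type of stay is not given. Expected outcomes speaks of shortening stay without a number.

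**Conclusion.** The point holds as an inconsistency between endpoint definition and observation window, together with missing rules. Ventilation days are defined beyond the period in which data are collected. Length of stay is not defined at all, so it would be wrong to say that it is defined over the whole hospitalisation. Early deaths would count as short durations if the listed tests are applied directly.

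The estimated difference in total stay is pulled towards zero in every scenario examined. Power is nearly unchanged for assumed medians of about 3 to 5 days. It drops by 12 points (92% to 80%) at 10 versus 8 days and by 34 points (57% to 23%) at 15 versus 13. These sizes rest on the log-normal assumption and the chosen medians; the documents cannot say which row applies. The distortion from deaths can go either way, depending on which arm has more early deaths.

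It would go too far to conclude that the length-of-stay objective cannot be answered. The objective asks for any effect, and a comparison restricted to Day 7 can show one, as the 16 versus 9 row does. What Day 7 data cannot give is the effect on total stay or total ventilation time. The matter should be corrected, but it concerns secondary endpoints only.

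**What to change.** First define length of stay: ICU, hospital or both, and the moment it starts. Then choose one of two routes.

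1. **Keep the 7-day horizon.** Redefine the endpoints as days alive and free of invasive ventilation, and days alive and out of ICU, up to Day 7, with deaths in that window scored 0. State the same window for NIV days, which include the allocated prophylactic sessions and so are better described than scored as a benefit or harm. Limit conclusions to seven days. The cost is wording only. The downside is a composite in which death and duration are mixed, so the components should be reported too. If many patients are still in ICU at Day 7, scores pile up at 0 and lost power is not recovered.

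2. **Keep total durations.** Take ICU-discharge, hospital-discharge and last-ventilation dates from the existing hospital file for every patient, and state how deaths are handled, for example discharge alive with death as a competing event. The cost is a few extra date fields and no added visit. If these dates are already recorded, the plan need only say so.

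Either way, the analysis section should say how a patient still ventilated or in ICU at the end of the window is scored, so that unfinished stays are not treated as missing and dropped.
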